4.2 Scientific Rationale for Study Design

The primary objective of this study is to evaluate the effect of zibotentan 1.5 mg and dapagliflozin 10 mg in combination, compared to dapagliflozin 10 mg monotherapy, on UACR. The secondary objectives are to determine the change in UACR for zibotentan 0.25 mg combined with dapagliflozin 10 mg versus dapagliflozin 10 mg monotherapy, and the change in office systolic and diastolic BP for doses of zibotentan combined with dapagliflozin 10 mg versus dapagliflozin 10 mg monotherapy, to characterise the dose-response relationship of the different zibotentan/dapagliflozin doses and the UACR reduction, and to determine the effect of zibotentan and dapagliflozin in combination versus dapagliflozin 10 mg on eGFR.

UACR was chosen as a surrogate for renal outcomes based on the analyses presented at the 2018 National Kidney Foundation (NKF)/FDA workshop on endpoints in CKD, which noted a strong and consistent relationship between change in UACR and the clinical outcome of kidney disease progression (Levey et al, 2020).

The study will evaluate general safety and tolerability of treatment with zibotentan and dapagliflozin in combination, compared with dapagliflozin monotherapy, with special focus on hypotension and hospitalisations due to HF. Changes in fluid-related measures (weight gain or BNP) that meet the defined threshold (Section 7.1) will be reported as an event of special interest.

Exploratory objectives include assessment of PK, change in body weight, dose/exposure of zibotentan relative to safety and PD variables, change in plasma/serum concentrations of K⁺, Na⁺, uric acid, BUN, fasting plasma glucose, haematocrit, haemoglobin, ET-1, ELDP, CT-proET-1, and copeptin levels, change in cardiovascular biomarkers in blood (NT-pro-BNP, BNP), and change in body fluid volume and distribution status. In addition, plasma, serum and urine samples will be collected and stored for potential future exploratory research aimed at exploring biomarkers relevant to cardiorenal mechanisms, inflammation, and fibrosis. Optional blood samples will be collected and stored for genetic research (according to each country's local and ethical procedures).

This study is randomised and double-blinded to prevent bias in treatment allocation and in the subjective assessment of effect of the study intervention in the intended study population. A randomised, blinded, multicentre, active-controlled study design is considered the best design to achieve the objectives of the study, from both safety and efficacy perspectives.

4.3 Justification for Dose

Zibotentan

Zibotentan doses of 0.25, 1.5, and 5 mg (hereafter referred to as low, intermediate, and high dose, respectively) were initially selected to characterise the dose-UACR response relationship for zibotentan. Predictions were made using an exposure-UACR response model of clinical data from other ETA receptor antagonists, taking into account differences in PK and potency between the different compounds. Based on this model, 5 mg zibotentan was predicted to achieve a maximal UACR response. In participants with severe renal impairment, a dose of 5 mg will result in plasma exposure similar to that of 10 mg in subjects with normal renal function. Since 10 mg was associated with an increased fluid retention risk in earlier clinical studies, 5 mg was initially selected to be the highest dose used in this study involving a participant population with renal impairment. Based on the rate of fluid retention observed in an ad hoc safety interim analysis, randomisation to 5 mg zibotentan (both monotherapy and in combination with dapagliflozin) has been discontinued. The zibotentan 1.5 mg dose is predicted to cause less fluid retention than 5 mg, while at the same time producing meaningful UACR response, according to the model predictions. The zibotentan 0.25 mg dose was selected to be a minimally clinically relevant dose because it is predicted to produce a 20% or less reduction in UACR in addition to that with dapagliflozin.

Dapagliflozin

Dapagliflozin 10 mg is the approved dose for T2DM, CKD, and HF. 10 mg is the dose tested in DAPA-CKD for patients with CKD and an eGFR > 25 mL/min/1.73m² (NCT03036150).

Based on available preclinical and clinical data, the risk for metabolic drug-drug interactions between zibotentan and dapagliflozin is regarded as low.

4.4 End of Study Definition

Participants are considered to have completed the study if they have completed all phases of the study including the follow-up visit as shown in the SoA ([Table 1](#)).

The end of the study is defined as the date of the last visit of the last participant in the study.

5 STUDY POPULATION

Prospective approval of protocol deviations to recruitment and screening criteria, also known as protocol waivers or exemptions, is not permitted.

5.1 Inclusion Criteria

Participants are eligible to be included in the study only if all of the following criteria apply:

Age

- 1 Participant must be 18 years of age or older at the time of signing the informed consent.

Type of Participant and Disease Characteristics / Laboratory Parameters

- 2 Diagnosis of CKD, defined as:
 - (a) eGFR (CKD-EPI) ≥ 20 mL/min/1.73 m² (by CKD-EPI formula, see Section 8.1.2.2)
AND
 - (b) Urine albumin to creatinine ratio (UACR) ≥ 150 and ≤ 5000 mg albumin/g creatinine, based on a single first morning void spot urine sample at screening.

Medical Treatment

- 3 No current or prior (within 1 month of screening) medical treatment with an SGLT2i or any FDC with SGLT2i (such as SGLT2i + metformin).
- 4 If ACEi and/or ARB and/or MRA are prescribed, the dose must be stable ≥ 4 weeks before screening. Participants who have been deemed unable to tolerate ACEi or ARB therapy due to allergy or complications can be enrolled.
- 5 No current or prior treatment within 6 months prior to screening with cytotoxic therapy, immunosuppressive therapy or other immunotherapy for primary or secondary kidney disease.

Weight

- 6 Body mass index (BMI) ≤ 40 kg/m².

Sex

- 7 Male or female of non-childbearing potential.

Reproduction

- 8 Female participants must have a negative pregnancy test at screening, must not be lactating, and must be of non-childbearing potential, confirmed at screening by fulfilling one of the following criteria:
 - (a) Postmenopausal defined as amenorrhoea for at least 12 months or more following cessation of all exogenous hormonal treatments and FSH and LH levels in the postmenopausal range.

- (b) Documentation of irreversible surgical sterilisation by hysterectomy, bilateral oophorectomy, or bilateral salpingectomy but not tubal ligation.
- 9 Male participants must be surgically sterile, abstinent, or in conjunction with a female sexual partner, using a highly effective method of contraception for the duration of the study (from the time they sign consent) and for 3 months after the last dose of investigational product to prevent any pregnancies. Male study participants must not donate or bank sperm during this same time period (see Section 8.3.8.2).

Methods that can achieve a failure rate of less than 1% per year when used consistently and correctly are considered highly effective birth control methods such as:

- Combined (oestrogen and progesterone containing) hormonal contraception associated with inhibition of ovulation:
 - Oral.
 - Intravaginal.
 - Transdermal.
- Progesterone-only hormonal contraception associated with inhibition of ovulation:
 - Oral.
 - Injectable.
 - Implantable.
- Intrauterine device (IUD).
- Intrauterine hormone-releasing system (IUS).
- Bilateral tubal occlusion of female partner.
- Male vasectomy.
- True sexual abstinence.

True abstinence refers to: when this is in line with the preferred and usual lifestyle of the participant. Periodic abstinence (eg, calendar, ovulation, symptom-thermal, post-ovulation methods), declaration of abstinence for the duration of a trial, and withdrawal are not acceptable methods of contraception.

Informed Consent

- 10 Capable of giving signed informed consent, as described in [Appendix A](#), which includes compliance with the requirements and restrictions listed in the informed consent form (ICF) and in this protocol.
- 11 Provision of signed and dated, written ICF prior to any mandatory study-specific procedures, sampling, and analyses.

- 12 Provision of signed and dated written Genetic informed consent prior to collection of samples (optional) for genetic analysis.

5.2 Exclusion Criteria

Participants are excluded from the study if any of the following criteria apply:

Medical Conditions

- 1 Minimal change disease, unstable rapidly progressing renal disease, and/or renal disease requiring significant immunosuppression, autosomal dominant or autosomal recessive polycystic kidney disease.
- 2 Participants with NYHA functional HF class III or IV.
- 3 Acute coronary syndrome (ACS) events within 3 months prior to screening.
- 4 Participants with a BNP ≥ 200 pg/mL or NT-proBNP ≥ 600 pg/mL (BNP ≥ 400 pg/mL or NT-proBNP ≥ 1200 pg/mL, respectively, if associated with atrial fibrillation) measured by local laboratory at screening (Visit 1).
- 5 Participants with unstable HF requiring hospitalisation for optimisation of HF treatment and/or who have not been stable on HF therapy within 6 months prior to screening.
- 6 Heart failure due to cardiomyopathies that would primarily require other specific treatment: eg, cardiomyopathy due to pericardial disease, amyloidosis or other infiltrative diseases, cardiomyopathy related to congenital heart disease, primary hypertrophic cardiomyopathy, cardiomyopathy related to toxic or infective conditions (ie, chemotherapy, infective myocarditis, septic cardiomyopathy).
- 7 High output HF (eg, due to hyperthyroidism or Paget's disease).
- 8 Heart failure due to primary cardiac valvular disease/dysfunction, severe functional mitral or tricuspid valve insufficiency, or planned cardiac valve repair/replacement.
- 9 Participants with uncontrolled diabetes mellitus (HbA1c $> 12\%$).
- 10 Participants with T1DM.
- 11 Hyponatremia, defined as serum $\text{Na}^+ < 135$ mmol/L at the time of screening (Visit 1).
- 12 Intermittent or persistent second or third degree atrioventricular (AV) block after sinus node dysfunction, with clinically significant bradycardia or sinus pause when not treated with pacemaker.
- 13 Prolonged QT interval (QTcF > 470 ms) on ECG at screening (Visit 1) or randomisation visit (Visit 2), known congenital long QT syndrome or history of QT prolongation associated with other medications.
- 14 History of any life-threatening cardiac dysrhythmia (continuous or paroxysmal or uncontrolled ventricular rate in participants with atrial fibrillation or atrial flutter).

- 15 Cardiac surgery or non-elective percutaneous coronary interventions (PCI/TAVI) (within 3 months) or open chest coronary artery bypass grafting or valvular repair/replacement (within 3 months) prior to screening or is planned to undergo any of these procedures after randomisation.
- 16 Heart transplantation or left ventricular assist device at any time.
- 17 Kidney or any organ transplantation.
- 18 History or ongoing allergy/hypersensitivity, as judged by the investigator, to SGLT2i (eg, dapagliflozin, canagliflozin, empagliflozin) or drugs with a similar chemical structure to zibotentan.
- 19 Any clinically significant disease or disorder (eg, cardiovascular, gastrointestinal, liver, renal, neurological, musculoskeletal, endocrine, metabolic, psychiatric, major physical impairment) which, as judged by the investigator, might put the participant at risk because of participation in the study, or probable alternative primary reason for participant's symptoms in judgment of investigator, including but not limited to:
 - (a) Isolated pulmonary arterial hypertension (defined as mean PAP \geq 25 mmHg at rest) or right ventricular failure; in the absence of left-sided HF.
 - (b) Anaemia defined as haemoglobin (Hb) level $<$ 100 g/L or 10 g/dL at screening (Visit 1).
 - (c) Severe chronic obstructive pulmonary disease (COPD) or other lung disease including but not limited to pulmonary fibrosis requiring chronic O₂ therapy, regular nebuliser use, or oral steroid therapy.
- 20 Stroke, transient ischemic attack, carotid surgery, or carotid angioplasty within previous 3 months prior to screening.
- 21 Active malignancy requiring treatment (except for basal cell or squamous cell carcinomas of the skin) and malignancies 5 years prior to screening.
- 22 Severe hepatic impairment (Child-Pugh class C Hepatic impairment), aspartate transaminase [AST] or alanine transaminase [ALT] $>$ 2x the upper limit of normal [ULN]; or total bilirubin $>$ 2x ULN at time of screening. An isolated increase in bilirubin in participants with known Gilbert's syndrome is not a reason for exclusion.
- 23 Participants with newly detected pathological laboratory values or an ongoing disease condition requiring investigation and/or initiation or adjustment of current treatment (in the opinion of the investigator).
- 24 Drug or alcohol abuse, either current or within 12 months before screening.
- 25 Positive hepatitis C antibody or hepatitis B virus surface antigen at screening.
- 26 Positive human immunodeficiency virus (HIV) test.
- 27 Participants treated with strong or moderate CYP3A4 inhibitor or inducer.

- 28 Any condition outside the renal and CV disease area, such as but not limited to malignancy, with a life expectancy of less than 2 years based on investigator's clinical judgment.
- 29 Confirmation of COVID-19 infection:
 - (a) Participant has a positive test result for SARS-CoV-2 during screening. Participants who are not hospitalised for COVID-19 infections can be re-screened 4 weeks after they have recovered.
 - (b) Participant has been previously hospitalised with COVID-19 infection.
- 30 Ejection fraction < 50% measured by ECHO at screening.

Prior/Concurrent Clinical Study Experience

- 31 Participation in another clinical study with an investigational product administered in the last 3 months prior to screening.

Other Exclusions

- 32 Involvement in the planning and/or conduct of the study (applies to both AstraZeneca staff and/or staff at the study site).
- 33 Judgment by the investigator that the participant should not participate in the study if the participant is unlikely to comply with study procedures, restrictions, and requirements.
- 34 Previous randomisation into the present study.
- 35 Plasma donation within 1 month of the visit at the clinic or any blood donation/blood loss > 500 mL during the 3 months prior to any visit at the clinic.
- 36 Male participant in a sexually active relation with pregnant or breastfeeding partner.

Genetic Sampling (Optional)

Participants can decline to participate in the genetic research and may still participate in the study. Exclusion from this optional genetic research may be for any of the exclusion criteria specified for the main study or any of the following:

- 37 Previous allogeneic bone marrow transplant.
- 38 Non-leukocyte depleted whole blood transfusion within 120 days of genetic sample collection.

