1.3 Schedule of Activities
Table 1 Schedule of Activities

Procedure	Screening	Interventional period							Follow-up	Notes	Details in CSP Section/Appendix
		1	2	3	4	5	6	7 (ED)			
Visit	1	2	3	4	5	6	7 (ED)	8			
Week	-4	0	1	3	6	9	12	14			
Day	-28	1	8	22	43	64	84	98			
Day Visit Window	+7/ -14		±1	±2	±2	±2	±2	±3			
Informed consent	X									Section 5.1; Appendix A 3	
Inclusion and exclusion criteria	X	X							Recheck clinical status before randomisation.	Sections 5.1 and 5.2	
Screening in IRT/RTSM	X									Section 6.3	
Randomisation in IRT/RTSM		X							Diaries will be given to the participants and they will be asked to fill in the dose intake information (date and time) at home.	Section 6.3 and 6.4	
Routine clinical procedures											
Demography and baseline characteristics (smoking history and alcohol consumption included)	X									Sections 5.1 and 5.2	
Physical examination	X	X	X	X	X	X	X	X	A complete physical examination will be done at screening, randomisation and Week 12. A brief physical examination will be done at Weeks 1, 3, 6, 9, 14.	Section 8.2.1	

Procedure	Screening	Interventional period							Follow-up	Notes	Details in CSP Section/Appendix
		1	2	3	4	5	6	7 (ED)			
Visit	1							8			
Week	-4	0	1	3	6	9	12	14			
Day	-28	1	8	22	43	64	84	98			
Day Visit Window	+7/ -14		±1	±2	±2	±2	±2	±3			
Medical/ surgical history, which includes substance usage and family history of premature cardiovascular disease	X								Substances: drugs, alcohol, tobacco, and caffeine	Sections 5.1 and 5.2	
Height	X									Sections 5.1, 5.2 and 8.2.1	
Serology (HIV I and II, Hepatitis B surface antigen, Hepatitis C virus antibody, central laboratory)	X								Results need to be available before randomisation.	Section 8.2.4	
FSH/LH and serum pregnancy test (females only, central laboratory)	X								Results need to be available before randomisation.	Section 8.2.4	
Local test for SARS-CoV-2	X								Testing is also required if participants show COVID-19 symptoms during the study.	Section 8.2.4	
Concomitant medication	X	X	X	X	X	X	X	X		Section 6.5	
Efficacy assessments											
Spot urine from first morning void: albumin and creatinine (central laboratory)	X								Results need to be available before randomisation. A single sample for analysis is sufficient at screening.	Section 8.1.1	

Procedure	Screening	Interventional period						Follow-up	Notes	Details in CSP Section/Appendix
		2	3	4	5	6	7 (ED)			
Visit	1						7 (ED)	8		
Week	-4	0	1	3	6	9	12	14		

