6.5 Concomitant Therapy

Any medication or vaccine (including over-the-counter or prescription medicines, vitamins, and/or herbal supplements) that the participant is receiving at the time of screening or receives during the study must be recorded along with:

- Reason for use.
- Dates of administration including start and end dates.
- Dosage information including dose and frequency.

The Study Physician should be contacted if there are any questions regarding concomitant or prior therapy.

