6.5.1 Prohibited Concomitant Medications

The medications and supplements listed below are prohibited from the time of consent and for the duration of the study. Participants taking any of these medications at the time of randomisation cannot be included into the study:

- SGLT2i.
- Direct renin inhibitor (eg, Aliskiren).
- Cyclosporin or tacrolimus.
- Receiving cytotoxic therapy, immunosuppressive therapy, or other immunotherapy for primary or secondary renal disease within 6 months prior to screening.

In addition to the above, the following medications cannot be initiated or any changes to dose made after the participant has consented, and until the participant has completed the study (or discontinued / withdrawn participation):

- ACEi.
- ARB.
- ARNi.
- MRA.

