6.5.3 Background Standard of Care Therapy

Prescribed SoC treatment for CKD (eg, ACEi and/or ARB) should be stable for at least 4 weeks prior to screening (see inclusion criterion #4) and remain stable during the study.

It is preferable that any background medical therapy (eg, antidiabetic or antihypertensive therapy [including diuretics] or therapy with statins) does not change during study intervention; ie, between the screening visit and the last dose of investigational product. However, if this is necessary, the participant does not need to be withdrawn from study intervention.

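### Strong and moderate CYP3A4 inhibitors and inducers are barred at entry but appear in neither on-study list in Protocol 6.5.1, so no explicit site rule stops one being started after randomisation (minor conduct and safety inconsistency)

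*Protocol*

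**What the plan says.** - **Entry.** Protocol 5.2, criterion 27, excludes "Participants treated with strong or moderate CYP3A4 inhibitor or inducer". It gives no washout period and says nothing about the treatment period. The Schedule of Activities marks eligibility at Visits 1 and 2 only, with the note "Recheck clinical status before randomisation".
- **On study.** Protocol 6.5.1 opens its first list with "The medications and supplements listed below are prohibited from the time of consent and for the duration of the study". That list covers SGLT2 inhibitors, direct renin inhibitors, cyclosporin or tacrolimus, and cytotoxic or immunosuppressive therapy for renal disease. A second list bars starting, or changing the dose of, ACE inhibitors, ARBs, ARNi and MRAs. CYP3A4 inhibitors and inducers are in neither.
- **Other medication rules.** Protocol 6.5 says "The Study Physician should be contacted if there are any questions regarding concomitant or prior therapy". Protocol 6.5.3 prefers background therapy to stay unchanged, then adds "However, if this is necessary, the participant does not need to be withdrawn from study intervention". Neither section mentions CYP3A4.
- **Analysis.** SAP 4.8 repeats the two lists and provides for a medical review of which medications count as prohibited. Under SAP 4.10.2.1, use of a prohibited medication is an intercurrent event after which UACR is set to missing. SAP 4.5.2 makes it important deviation 3, and SAP 4.6 removes anyone with an important deviation from the Per Protocol Analysis Set (PPS).

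**The concern.** The sponsor judged this class unsuitable on Day 1, and nothing explains why it becomes acceptable on Day 2. It also looks like an oversight, because other entry rules on drug classes have an on-study counterpart. Inclusion criterion 3 ("No current or prior (within 1 month of screening) medical treatment with an SGLT2i or any FDC with SGLT2i") is matched by the SGLT2 inhibitor ban, criterion 4 by the bar on starting or changing renin-angiotensin agents and MRAs, and criterion 5 by the ban on cytotoxic and immunosuppressive therapy.

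What is at stake is zibotentan exposure. Protocol 4.3 notes that "10 mg was associated with an increased fluid retention risk in earlier clinical studies" and that, in severe renal impairment, "a dose of 5 mg will result in plasma exposure similar to that of 10 mg in subjects with normal renal function". Randomisation to 5 mg was stopped because of fluid retention. Participants are enrolled down to an eGFR of 20, so some already have raised exposure. If criterion 27 exists because CYP3A4 inhibition raises zibotentan exposure, the protocol leaves an avoidable route to that exposure open.

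**Working it through.** **1. Text comparison.** CYP3A4 modulators appear in the entry exclusions, in neither of the two lists in Protocol 6.5.1, in neither of the two copies in SAP 4.8, and in none of the stopping rules in Protocol 7.1. The interaction statement in Protocol 4.3 covers only zibotentan with dapagliflozin. The gap is in the text.

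**2. Exposure margin.** Assume exposure proportional to dose, and take the two-fold rise in severe renal impairment from Protocol 4.3.
- 1.5 mg to match 5 mg at the same renal function: 5 / 1.5 = 3.3-fold.
- 1.5 mg in severe renal impairment to match 10 mg in normal function: 10 / (2 × 1.5) = 3.3-fold.
- 0.25 mg to match 5 mg: 5 / 0.25 = 20-fold.
- The monotherapy arm receives no zibotentan.

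The documents give no CYP3A4 fold-change to set against these margins.

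**3. Effect on the UACR comparison.** The documents give no uptake, course length or effect per user, and the SD is redacted, so all four are assumptions: uptake 2–5%, one course of 7–14 days in the 84-day period, a change of 0.1–0.3 log(UACR) while on the drug, and an SD of 0.6–1.0. Arm sizes (166 and 83) and 150 evaluable per main arm come from Protocol 9.2.
- Ever exposed: 166 × 0.02 to 0.05 = 3.3 to 8.3 on 1.5 mg; 83 × 0.02 to 0.05 = 1.7 to 4.2 on 0.25 mg.
- On the drug at Week 12: 0.02 × 7/84 = 0.17% to 0.05 × 14/84 = 0.83%, which is 0.3 to 1.4 of 166.
- Shift in the 1.5 mg comparison: 0.00167 × 0.1 = 0.00017 to 0.00833 × 0.3 = 0.0025 log units, or 0.02% to 0.25% on the ratio scale.
- Standard error: SD × √(2/150) = 0.069 (SD 0.6) to 0.115 (SD 1.0).
- Shift relative to the standard error: 0.00017/0.115 = 0.1% to 0.0025/0.069 = 3.6%.

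Inhibitors and inducers would partly offset each other, reducing this further.

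**4. What simply adding the class to 6.5.1 would do.** Its use would become an intercurrent event. If all 2–5% of users in both arms lost Week 12, the standard error would rise by up to 1/√0.98 − 1 = 1.0% to 1/√0.95 − 1 = 2.6%. The same participants would have deviation 3 and leave the PPS. That cost is out of proportion to a shift of at most 0.0025 log units.

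**The case against.** The strongest reply is that the documents show no harm. Neither states that CYP3A4 affects zibotentan; detailed pharmacology is left to the Investigator's Brochures. The exposure margin is wide. Protocol 7.1 stops treatment for BNP rises, weight and body-water gain, heart failure and symptomatic hypotension, and allows discontinuation on general safety judgement. Section 8 sends emerging safety concerns to the sponsor at once, and home weight is monitored (8.2.2). The omission may also be deliberate: every item in 6.5.1 plausibly acts on the kidney or albuminuria, and the list drives the estimand, so an exposure-only class might belong solely in the entry criteria.

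Most of this stands, and it is why the point is minor. It does not remove the gap. The general clauses respond to a problem once seen; none tells a site not to start the drug. A site reading a list without the class has no prompt to call the Study Physician. If the restriction is meant for entry only, the protocol does not say so.

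Two stronger readings are tempting and are not supported:
- A reader might infer that such use adds unflagged noise to the exposure-response modelling in SAP 4.10.2.7. Medications are recorded with dates and dose (Protocol 6.5) and listed by participant (SAP 4.8), and plasma zibotentan is sampled in all participants at several on-treatment visits. A short course might fall between samples, but it would still be on record.
- A reader might infer that the analysis cannot recognise such use. The medical review in SAP 4.8 and the alternative wording of deviation 3 already allow it to be classified. That review acts on outputs, however, and not on prescribing.

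**Conclusion.** The inconsistency is real and minor: a class barred at entry has no explicit on-study rule. It concerns conduct and participant safety. Under the assumptions in step 3, the primary UACR comparison moves by at most 0.0025 log units, or 3.6% of one standard error, so a reader should not infer bias in the primary result.

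Nor do the documents support saying that a participant on 1.5 mg would reach the exposure of the discontinued 5 mg dose. That needs a 3.3-fold rise under dose proportionality, and any CYP3A4 effect on zibotentan is inferred from criterion 27 alone. No number of additional fluid events can be given, because the documents contain no event rate at 1.5 mg.

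**What to change.** - **Protocol 6.5.** Add a separate on-study restriction, outside the 6.5.1 lists: strong and moderate CYP3A4 inhibitors and inducers should not be started during treatment. If a short course is unavoidable, the site contacts the Study Physician and withholds only the blinded zibotentan/placebo capsule, as 6.6 allows, while continuing the dapagliflozin tablet. The capsule and tablet are separate products (6.1.1), so this keeps the blind, and in the monotherapy arm only placebo is interrupted. Withholding both would needlessly remove dapagliflozin. The 21% UACR reduction cited for it in Protocol 2.2 is −ln(0.79) = 0.24 log units, within the 0.1–0.3 range assumed for the problem itself.
- **SAP 4.8 and 4.5.2.** State that such use is flagged and listed, but is not by itself a prohibited-medication intercurrent event or an important deviation that excludes the participant from the PPS. Keeping the class out of 6.5.1 leaves the estimand text as it is.
- If the entry-only restriction is intended, one sentence saying why would be enough.

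**Cost.** A short paragraph in the protocol and a sentence or two in the SAP, with no new data collection. A few participants would need an alternative agent or a brief capsule interruption. With the assumptions above, at most 0.83% of the 1.5 mg arm would be off the capsule at Week 12, diluting the zibotentan effect by at most 0.83% of its value. A 14-day interruption leaves capsule compliance at 70/84 = 83%, above the 80% threshold in SAP 4.9.
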